## 9.10. Occupational Safety

There are no known occupational safety risks to staff. The Material Safety Data Sheet will be made available where required by local regulations.

## 10. CONCOMITANT MEDICATIONS AND NON-DRUG THERAPIES

### 10.1. Recording Prior and Concomitant Medication

All relevant medication taken within 4 months of screening should be recorded in the eCRF along with all relevant medication taken from the start of the screening period until the final follow-up visit (Section [6.2.1.3](#)).

At a minimum the following information will be collected:

- Generic name
- Dose
- Frequency
- Date started
- If ongoing (or if not, then the date stopped will be recorded)
- Reason for taking the medication

Study Number: INVEX-CLIN-IIH-301 Protocol	Compound No.: Presendin
	Version: 3.0

### **10.1.1. Treatment Failure**

Rescue therapy can be initiated when there is a treatment failure. Since perimetric variability increases with increasing visual field damage, a two-tiered approach is used [[Wall, 2013](#)].

#### **10.1.1.1. Possible treatment failure**

Possible treatment failure is defined as those with baseline PMD between -2 and -3.5dB who experience a decline of > or equal to 2dB. In those with a baseline PMD between -3.5 and -7 dB, those who experience a decline of > or equal to 3 dB.

When a possible treatment failure is identified, perimetry, and if needed, other visual tests, should be repeated at an unscheduled visit.

#### **10.1.1.2. Definite treatment failure**

A definite treatment failure occurs when a patient with baseline PMD between -2 and -3.5dB experiences a decline of > or equal to 2dB which remains after repeat perimetry. Or in those with a baseline PMD between -3.5 and -7 dB who experience a decline of > or equal to 3 dB which remains after repeat perimetry.

These cases should be reviewed without delay by the IAC (who will review all visual and clinical data) to confirm or refute a definite treatment failure.

### **10.1.2. Rescue Therapy/Rescue Intervention for Progressive Visual Loss**

When a treatment failure occurs, rescue therapy can be initiated, in addition to study treatment, based on the medical judgement of the Investigator. Decisions should always be discussed with the IAC without delay and if possible before any action is taken, unless in the opinion of the Investigator there is no time to do so as it is judged to be a medical emergency. In all cases the final decision lies with the Investigator.

Patients showing progressive visual loss will be considered for rescue therapy with acetazolamide or an alternative diuretic. In cases where the visual loss is severe and “rapid”, and believed by the Investigator to necessitate surgical intervention, the intervention will be conducted in accordance with local emergency practice.

#### **10.1.2.1. Rescue Therapy for Headache**

If the Investigator wishes to alter the headache preventative medication (any drug can be considered), this decision should always be discussed with the IAC before any action is taken, unless in the opinion of the Investigator there is no time to do so as it is judged to

Study Number: INVEX-CLIN-IIH-301 Protocol	Compound No.: Presendin
	Version: 3.0

be a medical emergency. Use of headache preventative medication will be recorded at trial visits.

Use of acute headache analgesics is not considered as rescue medication and is permitted but must be documented in the headache diary (monthly analgesic use).

## **10.2. Prohibited Medications**

### **10.2.1. Prior to screening and randomisation**

- Treatment to lower ICP within 1 week prior to screening (e.g., acetazolamide, topiramate (including if used as a migraine preventative), diuretics, glucocorticoids (I.V., injectable steroids or oral (including dexamethasone and prednisolone)). (Nasal, inhaled, or topical steroids are allowed).
- Exposure to fluoroquinolones, lithium, vitamin A, or tetracyclines within 2 months of diagnostic LP
- Glucagon like peptide-1 receptor agonist within last 4 weeks prior to screening
- Warfarin
- Glucose-lowering medication COVID-19 vaccine within 2 weeks prior to screening
- Recreational or illicit drugs during screening period

Note: Use of headache preventative medication is allowed at enrolment (except for Topiramate). Changes to headache preventative medication during the trial should be made in consultation with the IAC – see section [10.1.2](#).

Study Number: INVEX-CLIN-IIH-301 Protocol	Compound No.: Presendin
	Version: 3.0

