#### **5.2. Eligibility Criteria**

##### **5.2.1. Inclusion Criteria**

Patients must not be enrolled unless they meet all the following criteria:

1. Age  $\geq 18$  years at the time of consent
2. Diagnosis of new IHH by consensus criteria (see Section 16.1, Appendix 1), including normal structural brain imaging (excluding features of raised intracranial pressure and incidentalomas), including either magnetic resonance venography or computed tomographic venography to exclude thrombosis and no evidence of a secondary causes of raised intracranial pressure
3. Newly diagnosed patients with screening commenced no more than 4 weeks after the diagnostic LP
4. Lumbar puncture opening pressure  $\geq 25$  cm cerebrospinal fluid (CSF) at diagnosis
5. Presence of bilateral papilloedema (Frisén grade  $\geq 1$ ). Verification of papilloedema by the OCT Reading Centre. Where there is uncertainty fundus photography and/or ultrasound scan (B scan) of the optic nerves should be conducted for evaluation by the Independent Adjudication Committee (IAC)
6. Perimetric Mean Deviation (PMD) defined as between -2 to -7 decibels (dB) in at least one eye. Eyes meeting this criteria will be defined as ‘study eyes’

Study Number: INVEX-CLIN-IIH-301 Protocol	Compound No.: Presendin
	Version: 3.0

7. Reproducible visual loss present on automated perimetry including no more than 15% false positive responses, (reliability confirmed by the Visual Field Reading Centre) in study eyes
8. Two or more headache days over the 7-day period prior to screening and also the patient must meet this criterion during the 7-day screening period
9. Females of childbearing potential must have a negative pregnancy test and must agree to use a highly effective birth control method (failure rate less than 1% per year when used consistently and correctly – see Section 16.7, Appendix 7 for further details) during the whole trial duration including the last follow-up visit (12 weeks after ceasing drug). Female patients who are lactating must agree to stop breast-feeding. Or female patients of non-childbearing potential (defined as pre-menopausal females with a documented tubal ligation or hysterectomy; or post-menopausal females defined as 12 months of amenorrhoea [in questionable cases a blood sample with simultaneous follicle stimulation hormone (FSH) 25-140 IE/L and oestradiol <200 pmol/L is confirmatory])

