### **5.2.2. Exclusion Criteria**

Patients will not be enrolled if they meet any of the following exclusion criteria:

IIH related exclusion criteria:

1. Presence of venous sinus thrombosis on brain imaging by either magnetic resonance or computerised tomographic venography
2. Previous IIH surgery including CSF shunt, optic nerve sheath fenestration or dural venous sinus stent or sub-temporal decompression
3. Previous bariatric surgery within the last 3 months or intention during the trial
4. Abnormal neurological examination (aside from papilloedema and consequent visual loss or sixth or seventh nerve palsy or palsies)
5. Treatment to lower ICP within 1 week prior to screening visit (e.g., acetazolamide, topiramate (including if used as a migraine preventative),

Study Number: INVEX-CLIN-IIH-301	Compound No.: Presendin
Protocol	Version: 3.0

diuretics, glucocorticoids (I.V., injectable steroids or oral (including dexamethasone and prednisolone)). (Nasal, inhaled, or topical steroids are allowed)

6. Use of any drugs known to cause intracranial hypertension, including exposure to fluoroquinolones, lithium, vitamin A, or tetracyclines within 2 months prior to diagnostic LP

Vision related exclusion criteria:

7. Any disease other than refractive error that causes visual loss in the study eyes. Where there is uncertainty this would be determined by the Independent Adjudication Committee [IAC]
8. Refractive error worse than +/- 6.00 sphere or worse than +/- 3.00 cylinder in study eyes. In addition, participants with myopia of worse than -6.00 D sphere but less than or equal to -8.00 D sphere are eligible if the subject wears a contact lens for all perimetry examinations with the appropriate correction
9. Inability to perform a reliable visual field examination as deemed by the Visual Field Reading Centre in the study eyes. Where there is uncertainty this would be evaluated by the Independent Adjudication Committee [IAC]

Headache related exclusion criteria:

10. Does not complete  $\geq 6$  days of electronic/paper trial diary during the 7-day screening period

Other exclusion criteria:

11. Untreated previously diagnosed obstructive sleep apnoea with historically recorded apnoea-hypopnea index greater than 15
12. Glucagon like peptide-1 receptor agonist within last 4 weeks prior to screening
13. COVID-19 vaccine within 2 weeks prior to screening

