#### **6.1.7. Unscheduled visit for repeat visual assessments**

Optional unscheduled visit for visual testing (HVF, OCT, LogMAR) for patients where there is concern about their visual decline or who perform inadequately or where there is technical failure (more than 15% false positive responses or inadequate performance indicated by the Visual Field Reading Centre for HVF; or OCT imaging not of satisfactory quality as determined by the OCT Reading Centre). Imaging only in the study eye(s).

- Optical coherence tomography Imaging

Study Number: INVEX-CLIN-IIH-301 Protocol	Compound No.: Presendin
	Version: 3.0

- Sites should initially check the scan quality. The OCT scan should go through the upload process to the OCT Reading Centre. The OCT scan will then be reviewed by the OCT Reading Centre for a full quality assessment. The report from the OCT Reading Centre will be sent to the site. Where the OCT is of insufficient quality it should be repeated as soon as possible at an unscheduled visit. Where the OCT processing is of insufficient quality it should be reprocessed as soon as possible by the site.
- Humphrey Visual Field (24-2 SITA-Standard)
  - Sites should initially check the performance quality of the HVF (to ensure no more than 15% false positives). The HVF should then be uploaded to the Visual Field Reading Centre without delay (an initial quality assessment takes place during the upload procedure). The HVF will then be reviewed by the Visual Field Reading Centre for a full quality assessment. Quality reports from the Visual Field Reading Centre will be received by the site. Where the visual field is of insufficient quality it should be repeated at an unscheduled visit without delay.
- Visual Acuity (LogMAR score)

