#### 6.2.1.3. Reporting of Prior and Concomitant Medication

Concomitant treatment is any medication or therapeutic intervention being continued by the patient at trial entry and any new medication received during the trial. Prior treatment

Study Number: INVEX-CLIN-IIH-301 Protocol	Compound No.: Presendin
	Version: 3.0

includes previous medications, treatments and interventions received in the past but no longer ongoing.

For this trial, only relevant prior concomitant medications within the last 4 months will be recorded. These include:

- Treatment to lower ICP (e.g., acetazolamide, topiramate (including if used as a migraine preventative), diuretics, glucocorticoids (I.V., injectable steroids or oral (including dexamethasone and prednisolone)). (Nasal, inhaled, or topical steroids are allowed)
- Headache preventative medication (including oral or botulism toxin A or monoclonal antibodies against CGRP or CGRP antagonists, or greater occipital nerve block)
- GLP-1 receptor agonist
- Warfarin
- Glucose lowering medication
- Recreational or illicit drugs

At every visit the Investigator or a qualified designee will ask the patient about relevant concomitant medication.

No new medication should be started during the trial, unless medically necessary. The patient should be advised to consult the Investigator or designee before taking any prescribed or over-the-counter medications. In the case of headache preventative medications or ICP lowering medications please see details in the rescue therapy section. Acute headache analgesics are permitted and should be reported in the diary.

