### 10.2.2. During the trial

- Treatment to lower ICP (e.g., acetazolamide, topiramate (including if used as a migraine preventative), diuretics, glucocorticoids (I.V., injectable steroids or oral (including dexamethasone and prednisolone)). (Nasal, inhaled, or topical steroids are allowed). These will all be considered rescue medication (Section 10.1.2) and the IAC consulted. Use will be considered a protocol deviation.
- If the Investigator alters the headache preventative medication (including oral or botulinum toxin A or monoclonal antibodies against CGRP or CGRP antagonists, or greater occipital nerve block) this will be considered headache rescue medication (Section 10.1.2) and the IAC consulted.
- Glucagon like peptide-1 receptor agonists
- Recreational or illicit drugs
- Warfarin
- Glucose-lowering medication
- Regarding COVID-19 vaccination, the risks of receiving or not receiving the vaccination have been considered in relation to the IMP and no additional risks are envisaged. Hence patients may choose to have or not have COVID-19 vaccination or booster during this trial.

The investigator should follow the cautions and guidance on the management of other concomitant medication or DDIs as detailed in section 9.2.5.2 (Drug-Drug Interactions) of the IB.

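### Protocol v3.0 bars drugs it names as causes of intracranial hypertension only around the diagnostic lumbar puncture; during the trial they are neither restricted nor named for recording

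*Protocol*

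**What the plan says.** All references are to protocol v3.0.

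- **Entry.** Exclusion criterion 6 (section 5.2.2) rules out use of any "drugs known to cause intracranial hypertension, including exposure to fluoroquinolones, lithium, vitamin A, or tetracyclines within 2 months prior to diagnostic LP". Section 10.2.1 repeats the bar: "Exposure to fluoroquinolones, lithium, vitamin A, or tetracyclines within 2 months of diagnostic LP". Inclusion criterion 2 (section 5.2.1) asks for "no evidence of a secondary causes of raised intracranial pressure".
- **During the trial.** Section 10.2.2 covers ICP-lowering treatment, changes to headache preventatives, GLP-1 receptor agonists, recreational or illicit drugs, warfarin, glucose-lowering medication and COVID-19 vaccination. It also gives a general pointer to the Investigator's Brochure: "The investigator should follow the cautions and guidance on the management of other concomitant medication or DDIs". The four named drugs or classes do not appear.
- **Recording.** Section 6.2.1.3 states: "For this trial, only relevant prior concomitant medications within the last 4 months will be recorded". It then lists six kinds of medication, introduced as inclusions, and this class is not among them. Section 10.1 adds "All relevant medication taken within 4 months of screening should be recorded in the eCRF" and refers back to 6.2.1.3 without adding drug names.
- **General safeguards.** Section 6.2.1.3 discourages new medication unless it is medically necessary and adds: "The patient should be advised to consult the Investigator or designee before taking any prescribed or over-the-counter medications". Section 6.1.7 provides an "Optional unscheduled visit for visual testing (HVF, OCT, LogMAR) for patients where there is concern about their visual decline".

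**The concern.** Every patient enters with papilloedema and with visual field loss in at least one eye. Intracranial pressure is the primary endpoint and treatment failure is a secondary one. As the lists stand, such a patient could be given a tetracycline or a fluoroquinolone, or start vitamin A, during the 24 weeks without a named breach and possibly without an eCRF entry.

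Two things would follow. The patient's vision could be put at avoidable risk, because nothing prompts the prescriber to look for another drug. A visual decline after such an exposure could also be taken for plain treatment failure. The Independent Adjudication Committee (IAC) confirms or refutes definite failures from the visual and clinical data (section 10.1.1.2), but it can weigh only what was collected. An exposure that nobody asked about cannot be restored at the analysis stage, so this belongs in the protocol and cannot be left to the SAP.

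**Working it through.** No figure in the plan bears directly on this point, so the main check is a comparison of lists.

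**Step 1. Each item of 10.2.1 against 10.2.2 and 6.2.1.3.**

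| Item in 10.2.1 | 10.2.2 (during trial) | 6.2.1.3 (recorded) |
|---|---|---|
| ICP-lowering treatment | treated as rescue and a deviation | named |
| Fluoroquinolones, lithium, vitamin A, tetracyclines | **not addressed** | **not named** |
| GLP-1 receptor agonists | banned | named |
| Warfarin | banned | named |
| Glucose-lowering medication | banned | named |
| COVID-19 vaccine | expressly permitted | not named |
| Recreational or illicit drugs | banned | named |

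Section 10.2.2 addresses six of seven items and 6.2.1.3 names five of seven. This class is the only one missing from both.

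**Step 2. Do the general rules fill the space?** The medical-necessity rule governs whether a new drug is started, not which one: an antibiotic for an infection can be necessary while the choice of class stays open. The Brochure pointer is to a section titled for drug-drug interactions; going by the title alone (the Brochure is not at hand), that concerns interactions with study drug rather than drugs that raise pressure by themselves. Section 12.1.3 puts measures taken to manage an adverse event in the source document and has them reported as the sponsor instructs; this secures source, not a medication entry in the eCRF. Recording under 6.2.1.3 turns on whether a site judges an unnamed short course relevant.

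**Step 3. Length of the unnamed period** (Table 1 and the Visit 10 rule). Day 1 to Day 169: 169 − 1 = 168 days. With the 14-day delay: 168 + 14 = 182 days. Criterion 6 also looks only backwards from the diagnostic LP. Screening may start up to 4 weeks later and last up to 10 days, so up to 28 + 10 = 38 further days before Day 1 fall outside its wording. Section 10.2.1 does not say the window runs only backwards and could be read to cover that interval, but not the treatment period.

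**Step 4. Does visual monitoring substitute?** It detects a decline after the event. Visits 6 to 9 are 28 days apart with ±5-day windows: 28 + 5 + 5 = 38 days at most between scheduled tests. Visit 9 to Visit 10: (169 + 14) − (141 − 5) = 183 − 136 = 47 days at most. Unscheduled visits can shorten this.

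**Step 5. Scale of the endpoint (assumption).** Section 1.1 expects about 5-10% to need more aggressive intervention. If that is taken as the failure rate, 0.05 × 240 = 12 and 0.10 × 240 = 24 patients fail. Failures are few, so an unexplained one is awkward to interpret. This says nothing about how often exposure would occur.

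**The case against.** The strongest reply is that the entry bar has its own purpose. It is anchored to the diagnostic LP and protects the idiopathic diagnosis, and that does not call for a mirrored ban later. That stands. A reader might infer that v3.0 contradicts itself; it does not. The recording list is not a strict mirror of the entry bars either, since COVID-19 vaccination is also absent from it.

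Second, the general rules already restrict new drugs, and the investigator who is consulted has applied criterion 6 to that same patient. The proposed line adds little beyond the class names and the request to look for an alternative. That is largely true, but the addition is what bears on drug choice. Prior users are mostly excluded already, so exposure would usually need a new start and should be uncommon.

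Third, most new antibiotic or lithium use would treat an adverse event and so be in source; medication is reviewed at each visit from Visit 2; the list in 6.2.1.3 is open-ended; and the IAC is not confined to eCRF categories. This reduces the recording gap. It does not close it: self-taken vitamin A need not be tied to any adverse event, and nothing asks sites to give exposure dates to the IAC.

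Finally, the body of v4.0 was not available for this check, so the gap may already be closed.

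**Conclusion.** The gap in v3.0 is real and narrow. Drugs the protocol itself names as causes of raised pressure are barred only around the diagnostic LP, while every other item in 10.2.1 is addressed for the trial period. The general rules reduce the gap but neither direct the choice of drug nor ensure an eCRF record. It looks like an oversight, since no reason is given for leaving this class out, but that is an inference.

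Two stronger readings are tempting and are not supported. One is bias in the treatment difference: allocation is randomised and blinded, and nothing suggests use would differ by arm. The other is a loss of power: the documents give neither an exposure rate nor a size of pressure rise, so none can be derived. The point is a low-cost improvement to vision safety and to the reading of treatment failures. It assumes that v4.0 has not already made the change.

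**What to change.** First check the v4.0 body. If the gap remains:

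1. Add to 10.2.2: *Drugs known to cause intracranial hypertension (fluoroquinolones, lithium, vitamin A, tetracyclines): avoid from the diagnostic LP through Visit 10 unless medically necessary with no suitable alternative.*
2. Add the class to the list in 6.2.1.3, so that exposure is asked about at the existing medication reviews, its dates are entered in the eCRF, and they are available to the IAC at treatment-failure review.

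How exposed patients are handled in the analysis can be left to the SAP. The cost is two lines in an amendment, one more medication category at visits that already review medication, and a small constraint on drug choice that the necessity clause keeps compatible with good care. Sample size and visit schedule are unaffected.

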### 10.2.2. During the trial

- Treatment to lower ICP (e.g., acetazolamide, topiramate (including if used as a migraine preventative), diuretics, glucocorticoids (I.V., injectable steroids or oral (including dexamethasone and prednisolone)). (Nasal, inhaled, or topical steroids are allowed). These will all be considered rescue medication (Section 10.1.2) and the IAC consulted. Use will be considered a protocol deviation.
- If the Investigator alters the headache preventative medication (including oral or botulinum toxin A or monoclonal antibodies against CGRP or CGRP antagonists, or greater occipital nerve block) this will be considered headache rescue medication (Section 10.1.2) and the IAC consulted.
- Glucagon like peptide-1 receptor agonists
- Recreational or illicit drugs
- Warfarin
- Glucose-lowering medication
- Regarding COVID-19 vaccination, the risks of receiving or not receiving the vaccination have been considered in relation to the IMP and no additional risks are envisaged. Hence patients may choose to have or not have COVID-19 vaccination or booster during this trial.

The investigator should follow the cautions and guidance on the management of other concomitant medication or DDIs as detailed in section 9.2.5.2 (Drug-Drug Interactions) of the IB.

